Rationale	According to WHO, more than 230 million major surgical procedures are carried out under general anaesthesia each year worldwide. Despite important technological advances, airway management remains a major challenge in anaesthesiology. Data from large prospective studies on current incidence of major peri-intubation adverse events are lacking in the anaesthesia setting, especially on outcomes such as peri-intubation cardiovascular collapse, severe hypoxemia, and cardiac arrest. These events are more common in case of difficulties with airway management so that first pass intubation failure significantly increases the risks. Moreover, it has been documented that even transient hypotension during general anaesthesia, may have long-term consequences and may be associated with a worse outcome in patients undergoing non-cardiac surgery. The primary aim of the study is to assess the current incidence of major peri-intubation adverse events during anaesthesia in patients undergoing elective or emergency surgery performed in the operating room (OR) and non-OR setting and in the setting of nonoperating room anaesthesia. The secondary aim is to assess the current practice of airway management during anaesthesia worldwide.		
Study design	International, multicentre, prospective cohort study		
Inclusion criteria	We will include all adult (≥ 18 years old) patients undergoing advanced airway management for general anesthesia in the operating room (OR) or non-operating room anaesthesia (NORA) locations.		
Exclusion	Airway management during cardiopulmonary resuscitation.		
criteria	Critically ill patients undergoing advanced airway management due to their underlying clinical condition		
Primary	At least one of the following major peri-intubation adverse events occurring within		
outcome	30 minutes from induction or up to surgical incision:		
	 Severe hypoxia (SpO₂ < 80%) Cardiovascular collapse (at least one of the following): Systolic arterial pressure < 65 mmHg Systolic arterial pressure < 90 mmHg for > 15 minutes Unplanned need of vasopressors or fluid load > 15 ml/kg to maintain the target blood pressure. Cardiac arrest 		

Emergency front of neck access (eFONA)		
Cannot intubate cannot oxygenate scenario (CICO)		
Unplanned need for ICU admission secondary to airway management related		
complications		
In-hospital mortality		
All centers will enroll all consecutive patients meeting study criteria up to 50 maximum		
patients for each center.		
Informed consent and admission data		
Demographic and clinical characteristics		
ng		
ııg		
ts,		
ri		

•	Advanced airway management-related complications (severe cardiovascular
	collapse, severe and mild hypoxemia, cardiac arrest, airway injury or any
	bleeding, aspiration of gastric contents, dental injury, emergency front of
	neck airway (FONA), cannot intubate cannot oxygenate scenario (CICO),
	unplanned need for ICU secondary to airway management complications)

- Extubation procedure.
- In hospital mortality

Sample size

Post-intubation hypotension has been reported in up to 10% of patients. We aim to collect data on 1000 major peri-intubation events during anesthesia therefore we plan to recruit a total of 10.000 patients. Considering 5% data lost, our final sample size will be of 10500 patients. We estimated an average number of 50 intubations/week at each center so we plan to recruit a total number of 210 centers.

Statistical analysis

We will report mean and standard deviation of normally distributed variables and we will compare them using the student T-test. We will report non-normally distributed variables as median and interquartile range, comparing them using the Mann-Whitney U test. Categorical variables will be expressed as proportion and compared using the Chi-square or Fisher exact test as appropriate. We will perform a bivariate analysis to identify variables associated with the composite outcome of major peri-intubation adverse events and significant variables will be then used to construct a multivariate logistic model in order to identify independent variables.

The following planned secondary analyses will be performed:

- Place of advanced airway management: OR vs outside OR
- Type of surgery: cardiac vs non-cardiac surgery, ear-nose-throat surgery, thoracic surgery
- Urgency of the procedure: planned intubation vs unplanned intubation
- Type of hypnotic drug used: propofol vs different drug
- Airway management procedure: difficult airway management vs not difficult
- Patient's condition:
 - ASA 1-2 vs ASA 3-4;
 - BMI<30 vs BMI>30;

A two-sided p-value < 0.05 will be considered statistically significant. Statistical analysis will be performed by R 3.6.2 (http://www.R-project.org)

Dipartimento Oncologia

RATIONALE

According to WHO, more than 230 million major surgical procedures are carried out under general anaesthesia each year worldwide[1]. Despite important technological advances, airway management remains a major challenge in anaesthesiology.

The National Audit Project 4, published in 2011, for the first time addressed the need to systematically collect information on major airway-related complications in both the anaesthesia and critical care settings. While in the critical care setting the report provided important insights for improvement, incidence of major adverse events such as death, brain damage and need for emergency surgical airway appeared underestimated in anaesthesia [2] so that for every case captured by NAP4 there may be another 720 potential airway events if we consider hypoxemia and cardiovascular collapse [3].

Traditionally, airway management in anaesthesia has been described as anatomically difficult as opposed to airway management in critical care defined as physiologically difficult.

Indeed, the general population of patients undergoing elective surgery, has normally an adequate physiology reserve to cope the perioperative stress and most airway related complications are the consequence of potential difficulties at mask ventilation or intubation due to specific anatomic features (e.g. prognathism, large tongue, obesity).

On the other hand, critically ill patients are prone to a higher airway-related risk due to their underlying hypoxemia, shock, acidosis which expose them to the high incidence of adverse events, especially cardiovascular collapse, recently reported in the INTUBE study cohort [4].

Data from large prospective studies on current incidence of major peri-intubation adverse events are lacking in the anaesthesia setting, especially on outcomes such as peri-intubation cardiovascular collapse, severe hypoxemia, and cardiac arrest [5][6].

These events are more common in case of difficulties with airway management so that first pass intubation failure significantly increase the risks [7][8]. Moreover, it has been documented that even transient hypotension during general anaesthesia, may have long-term consequences and may be associated with a worse outcome in patients undergoing non-cardiac surgery [9][10].

The primary aim of the study is to assess the current incidence of major peri-intubation adverse events during anaesthesia in patients undergoing elective or emergency surgery and in the setting of nonoperating room anaesthesia. The secondary aim is to assess the current practice of airway management during anaesthesia worldwide.

STUDY DESIGN

International, multicenter, prospective cohort study.

POPULATION

Inclusion criteria

We will include all adult (≥ 18 years old) patients undergoing advanced airway management for general anaesthesia in operating room or non-operating room anaesthesia (NORA) locations. We will include all the procedures both diagnostic and therapeutic, elective, or emergency that will require an advanced airways management (either tracheal intubation or SGA placement).

All potentially eligible patients will be identified by local investigators by screening the OR schedule and the procedures performed outside the OR.

Exclusion criteria

We will exclude the airway management during cardiopulmonary resuscitation. Critical patients undergoing advanced airway management in ED, wards or ICU, due to their underlying clinical condition will not be included in the study.

PRIMARY OUTCOME

At least one of the following major adverse events occurring within 30 minutes from induction or up to surgical incision:

Major adverse event:

- Severe hypoxia (SpO₂ < 80%)
- Cardiovascular collapse (at least one of the following):
 - Systolic arterial pressure < 65 mmHg
 - Systolic arterial pressure < 90 mmHg for > 15 minutes
 - Unplanned need of vasopressors and/or fluid load > 15 ml/kg to maintain the target blood pressure.
- Cardiac arrest

Blood pressure values should be confirmed in two consecutive measurements on non-invasive blood pressure monitoring or for 10 seconds on invasive monitoring system.

SECONDARY OUTCOMES

- Minor adverse events:
 - Moderate hypoxia (SpO₂ < 93%)
 - Airway injury
 - Clinically relevant bleeding
 - Oral aspiration of gastric contents
 - Dental injury
- Difficult facemask ventilation
- First pass success rate
- Early cardiovascular collapse
- Late cardiovascular collapse

OTHER OUTCOMES

- Unplanned need for ICU admission secondary to airway management related complications
- Emergency front of neck airway (eFONA)
- Cannot intubate cannot oxygenate scenario (CICO)
- In-hospital mortality
- Post-procedural severe hypertension
- Difficult procedure (more than 2 attempts)

DATA COLLECTION

Data will be collected real-time by an investigator not involved in airway management using either the paper or the electronic version of the case report form on the Redcap.

The following variables will be collected:

- Informed consent and admission data
- Demographic and clinical characteristics
- Type of procedure (time, setting, type of surgery, elective or emergency

- Airway evaluation (anticipated difficult airway management)
- Monitoring applied during the procedure
- Ongoing respiratory and hemodynamical support before intubation
- Patient's parameters
- Preoxygenation method and use of apnoeic oxygenation (position during preoxygenation, rapid sequence induction applied)
- Fraction of expired O₂ (FeO₂) at the end of preoxygenation
- Application of any apnoeic oxygenation method
- Application of rapid sequence induction intubation
- Drugs used for induction (molecules and doses)
- Elective method for advanced airway management
- Operator's characteristics
- Method used for the second (and following) attempt
- Method used for adequate tube placement confirmation
- Duration of airway management procedure
- Outcome of endotracheal intubation (total number of attempts, laryngoscopic view, minimum SpO₂ during laryngoscopy, need for LMA)
- Advanced airway management-related complications (severe cardiovascular collapse, severe and mild hypoxemia, cardiac arrest, airway injury or any bleeding, aspiration of gastric contents, dental injury, emergency front of neck airway (FONA), cannot intubate cannot oxygenate scenario (CICO), unplanned need for ICU secondary to airway management complications)
- Extubation procedure
- In-hospital mortality

Local investigators are expected to transfer all collected data into an electronic CRF (eCRF, Research Electronic Data Capture – RedCap). Each local investigator will be trained on how to use the eCRF and will receive a personalized username and password. Each patient will be coded through a patient identification number generated by the eCRF and no patient names or initials will be present on the paper CRF.

Data will be handled confidentially and the paper CRF will be stored behind a lock at each local site. Any source of information which may allow to link a record with a patient will be destroyed at the end of the monitoring phase.

STATISTICAL ANALYSIS

We will report mean and standard deviation of normally distributed variables and we will compare them using the student T-test. We will report non-normally distributed variables as median and interquartile range, comparing them using the Mann-Whitney U test. Categorical variables will be expressed as proportion and compared using the Chi-square or Fisher exact test as appropriate. We will perform a bivariate analysis to identify variables associated with the composite outcome of major peri-intubation adverse events and significant variables will be then used to construct a multivariate logistic model in order to identify independent variables.

The following planned secondary analyses will be performed:

- Place of intubation: OR vs NORA
- Type of surgery: cardiac vs non-cardiac surgery, ear-nose-throat surgery, thoracic surgery
- Urgency of the procedure: planned advanced airway management vs unplanned advanced airway management
- Type of hypnotic drug used: propofol vs different drug
- Airway management procedure: difficult airway management vs not difficult
- Patient's condition:
 - ASA 1-2 vs ASA 3-4;
 - BMI<30 vs BMI>30;

A two-sided p-value < 0.05 will be considered statistically significant. Statistical analysis will be performed by R 3.6.2 (http://www.R-project.org)

Sample size

Post-intubation hypotension has been reported in up to 10% of patients [11].

We aim to collect data on 1000 major peri-intubation events during anesthesia in order to include at least 10 putative variables associated with this event in planned analyses and sub-analyses, therefore we plan to recruit a total of 10.000 patients. Considering a 5% data lost, our final sample size will be of 10500 patients. We estimated an average number of 50 intubations/week at each centre so we plan to recruit a total number of 210 centres.

CENTRES RECRUITMENT

We will recruit academic and non-academic hospitals worldwide. Any centre that performs advanced airway management in the context of general anesthesia for either surgery or diagnostic/therapeutic procedures will be eligible for participation. Centers characteristics (academic vs non-academic, workload etc.) will be collected.

We will launch a website (www.stargate.com) and a social media channel (@stargate_study) where we will publish study information and documents (e.g. protocol, case report form, national coordinator list) which will be available for potentially interested investigators.

The project will be presented and a call for centres will be announced during international meetings of anesthesiology.

We will also apply for receiving the endorsement of international scientific societies in order to promote and enhance participation to this study.

PATIENTS RECRUITMENT

After obtaining the local approval, each center will select a start date and screening for patients' eligibility will start. In order to avoid selection bias while addressing study feasibility and balance across different participating centers, a maximum number of 50 patients from each center will be enrolled. To maintain data collection feasible, optimize enrolment of all consecutive patients, especially for high-volume centers, and balance number of enrolled patients across different centers, we suggest to focus screening for enrolment from a pre-defined number of operating rooms (3 to 5 according to local workload) up to the final enrollment of 40 patients/center in the anesthesia setting without any time limitation. All consecutive patients undergoing advanced airway management in the NORA setting will be screened up to the final enrollment of 10 patients/center without any time limitation. Local investigators will be involved in the screening of operating list of those selected areas.

Screening of all consecutive patients will involve all patients treated in the selected areas of each center. Screening and reporting of all consecutive treated patients will be interrupted only when the target number of patients/center will be reached.

PUBLICATION AND AUTHORSHIP POLICY

The main results of STARGATE study will be published in a peer—reviewed international medical journal. Authorship policy will follow the International Committee of Medical Journal Editors (ICMJE) recommendations. Authorship will be considered based on contributions to recruitment of patients, data acquisition and cleaning, analysis and interpretation of the data, manuscript writing, submission of national/local grants AND final approval of the version to be published AND agreement to be accountable for all aspects of the work, in ensuring that questions related to the accuracy or integrity of any part of the work are appropriately investigated and resolved.

Dipartimento Oncologia

Members of the Steering Committee will be part of the Writing Committee and listed as Authors. National Coordinators and particularly committed investigators fulfilling the previously exposed criteria will be part of the Writing Committee.

Each centre will designate local coordinators who will provide scientific and structural leadership in their centres. They will ensure that all local necessary ethical and regulatory approvals are obtained

before the start of patient inclusion. Local coordinators will guarantee the integrity of data collection and ensure timely completion of CRFs.

Local coordinators will be listed as study collaborators in proportion to the number of recruited patients at each center.

SECONDARY ANALYSES

After publication of the primary results, on request, the dataset will be available for investigators for secondary analyses, after submission of a substudy proposal which will be evaluated for approval by the Steering Committee after consideration of its scientific quality (i.e. originality and scientific priority).

Before submission, the final version of all manuscripts related to the STARGATE study dataset must be approved by the Steering Committee. The members of the Writing Committee will be authors of the publications derived from the STARGATE study dataset.

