APPENDIX 1 – TABLE WITH STUDY DEFINITIONS

Airway injury	Any detectable and clinically relevant injury attributable to tracheal intubation procedure (e.g bleeding, tracheal or bronchial tear or laceration)
Advanced airway management	The use of either a supraglottic airway device or tracheal intubation as airway management method to provide general anesthesia
Cannot Intubate Cannot Oxygenate Scenario (CICO)	Impossibility to achieve a successful tracheal intubation and adequate patient's oxygenation.
Cardiac arrest	Pulseless dysrhythmia occurring during/after advanced airway management
Cardiovascular collapse	 At least one of the following, occurring within 30 minutes from advanced airway management or up to surgical incision: SAP < 65 mmHg SAP < 90 mmHg for > 15 minutes or up to incision if it comes before 15 min Unplanned need of vasopressors and/or fluid load > 15 ml/kg to maintain the target blood pressure.
Early cardiovascular collapse	Any cardiovascular collapse event occurring up to 10 minutes from induction (or surgical incision, whichever come first)
Late cardiovascular collapse	Any cardiovascular collapse event occurring from 11 to 30 minutes from induction (or surgical incision, whichever come first)
Clinically relevant airways bleeding	Any sign or symptom of airways haemorrhage that meet at least one of the following criteria: • requiring medical intervention by a healthcare professional • leading to hospitalization or increased level of care • Prompting a face to face evaluation
Dental trauma	Fracture or avulsion of tooth during airway management

Difficult mask ventilation	Impossibility to provide adequate ventilation because of one or more of the following problems: inadequate mask seal, excessive gas leak, or excessive resistance to the ingress or egress of gas
Difficult tracheal intubation	Procedure requiring > 2 laryngoscopy attempts
Duration of the airway management procedure	Difference between time of confirmed airway device placement and preoxygenation start
Emergency front of neck access (eFONA)	Emergency need for invasive access to the patient's neck to provide adequate oxygenation (e.g. cricothyroidotomy, percutaneous tracheostomy, surgical tracheostomy).
Severe hypertension	Systolic arterial pressure > 180 mmHg
Attempt	Each time a device (SGA, laryngoscope, fiberscope) is introduced in patient's mouth/nose.
Moderate Hypoxia	SpO ₂ < 93%

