Oral aspiration of gastric contents	Presence of vomit at the glottic inlet visualised during airway management in a previously clear airway
Rapid Sequence Induction- Intubation	Administration of rapid-onset induction agents and muscle relaxant with no ventilation between induction and laryngoscopy
Severe Hypoxia	SpO ₂ < 80%
Unplanned need of vasopressor	Rescue administration of any vasopressor (either as a bolus or continuous infusion) due to hypotension after induction

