APPENDIX 2 - DETAILED DESCRIPTION OF MEASUREMENTS.

Blood pressure monitoring

Blood pressure monitoring is a standard of care during airway management. Either noninvasive or invasive blood pressure monitoring is required for enrolled patients.

Noninvasive blood pressure monitoring

In case of noninvasive blood pressure monitoring, an appropriate size cuff (relative to the patient's arm circumference) is wrapped around the upper arm of the patient and the interval is set up according to clinical practice.

For the purposes of the current study, the hypotensive event (i.e. SAP < 90 mmHg) should be observed in at least two consecutive measurements.

In case of placement of an arterial line and invasive blood pressure monitoring start by 30 minutes following induction, the reference monitoring method for study outcome identification is the noninvasive blood pressure in place at the start of the procedure.

Invasive blood pressure monitoring

If an arterial line is already in place before intubation and invasive blood pressure monitoring is the standard of practice for the procedure, arterial pressure values from invasive monitoring must be registered and reported in the case report form.

For the purposes of the current study, the hypotensive event (i.e. SAP < 90 mmHg) should be observed in at least two consecutive measurements registered 10 seconds apart.

REFERENCES

- [1] T. G. Weiser *et al.*, "An estimation of the global volume of surgery: a modelling strategy based on available data," *www.thelancet.com*, vol. 372, p. 139, 2008, doi: 10.1016/S0140.
- [2] T. M. Cook, N. Woodall, and C. Frerk, "Major complications of airway management in the UK: Results of the Fourth National Audit Project of the Royal College of Anaesthetists and the Difficult Airway Society. Part 1: Anaesthesia," *Br. J. Anaesth.*, vol. 106, no. 5, pp. 617–631, 2011, doi: 10.1093/bja/aer058.
- [3] T. M. Cook, "Strategies for the prevention of airway complications a narrative review," *Anaesthesia*, vol. 73, no. 1. Blackwell Publishing Ltd, pp. 93–111, Jan. 01, 2018. doi: 10.1111/anae.14123.
- [4] V. Russotto *et al.*, "Intubation Practices and Adverse Peri-intubation Events in Critically III Patients from 29 Countries," *JAMA J. Am. Med. Assoc.*, vol. 325, no. 12, pp. 1164–1172, Mar. 2021, doi: 10.1001/jama.2021.1727.

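### Appendix 1 times cardiovascular collapse from advanced airway management, while the primary outcome and the early/late collapse split run from induction

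*Protocol*

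**What the plan says.** The Primary outcome section counts a patient as having the outcome on "At least one of the following major adverse events occurring within 30 minutes from induction or up to surgical incision". The synopsis uses the same window, "30 minutes from induction or up to surgical incision". The listed events are severe hypoxia, cardiovascular collapse and cardiac arrest.

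The table of definitions in Appendix 1 gives cardiovascular collapse its own window: "occurring within 30 minutes from advanced airway management or up to surgical incision". Cardiac arrest is "Pulseless dysrhythmia occurring during/after advanced airway management", with no time limit.

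Elsewhere the clock starts at induction:
- Early collapse (Appendix 1): "Any cardiovascular collapse event occurring up to 10 minutes from induction (or surgical incision, whichever come first".
- Late collapse (Appendix 1): "Any cardiovascular collapse event occurring from 11 to 30 minutes from induction (or surgical incision, whichever come first".
- Unplanned vasopressor, itself a collapse criterion (Appendix 1): "Rescue administration of any vasopressor (either as a bolus or continuous infusion) due to hypotension after induction".
- Arterial line rule (Appendix 2, noninvasive monitoring): "In case of placement of an arterial line and invasive blood pressure monitoring start by 30 minutes following induction".

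Appendix 1 defines advanced airway management as the use of a supraglottic device or tracheal intubation. It names no moment at which this begins. No text says whether the Primary outcome section or Appendix 1 prevails.

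**The concern.** Collapse is part of the primary outcome, and the primary aim is an incidence. Early and late collapse are secondary outcomes, each defined as any collapse event that falls in an induction-based interval. They therefore sit under a parent definition whose time zero is different from their own.

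Two things follow. The same episode can be a primary event under the Primary outcome section and not be collapse under Appendix 1, or the reverse. And early plus late collapse need not sum to collapse. Data are recorded in real time by local investigators at a planned 210 centres, so nothing in the text prevents different sites from applying different rules.

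**Working it through.** No figure in the protocol needs to be reproduced here. The check is a comparison of time origins, followed by window arithmetic.

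**Step 1: the clocks side by side**

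| Place | Clock starts at | Clock ends at |
|---|---|---|
| Synopsis; Primary outcome section | induction | 30 min or incision |
| Appendix 1, cardiovascular collapse | advanced airway management | 30 min or incision |
| Appendix 1, early collapse | induction | 10 min or incision, whichever first |
| Appendix 1, late collapse | induction (from minute 11) | 30 min or incision, whichever first |
| Appendix 1, unplanned vasopressor | induction | not stated |
| Appendix 2, arterial line rule | induction | 30 min |
| Appendix 1, cardiac arrest | during or after airway management | not stated |
| Appendix 1, severe hypoxia | not stated (threshold only) | not stated |

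The collapse entry is the only one with a timed window that does not start at induction.

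**Step 2: where the windows differ**

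Let L be the minutes from induction to advanced airway management. The documents do not give L, so the values below are assumptions. In minutes after induction:
- Primary outcome window: 0 to 30.
- Appendix 1 collapse window: L to 30 + L.
- They disagree on 0 to L and on 30 to 30 + L.
- If incision at or before 30 minutes ends both windows, only 0 to L remains.

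| Assumed L | Start of window | End of window (no earlier incision) |
|---|---|---|
| 2 | 0–2 | 30–32 |
| 5 | 0–5 | 30–35 |
| 10 | 0–10 | 30–40 |

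**Step 3: two collapses at L = 5**

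- Confirmed systolic pressure below 65 mmHg at 3 minutes, resolved before the device is used. It lies inside the primary window and inside the early interval. On the Appendix 1 clock it is at 3 − 5 = −2 minutes, before the collapse window opens.
- Confirmed systolic pressure below 65 mmHg at 33 minutes in a procedure without incision. On the Appendix 1 clock it is at 33 − 5 = 28 minutes, so it is collapse. It is outside the primary window and is neither early nor late.

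**Step 4: cardiac arrest and severe hypoxia**

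- Arrest at 3 minutes with L = 5, before device use: inside the primary window, but arguably not during or after airway management.
- Arrest at 45 minutes: it meets the Appendix 1 entry, but that entry sets no window of its own. The limit in the Primary outcome section therefore applies and excludes it. This is not a conflict.
- Severe hypoxia: the entry gives only a threshold, so the Primary outcome section governs. There is no conflict.

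**Step 5: after the change**

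With induction as the single start, both windows are 0 to 30 and the discordant time is 0 minutes for any L.

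**The case against.** The strongest reply is that the intended rule is easy to recover. The Primary outcome section lists the collapse criteria itself under an induction window, and every other timed entry agrees with it. A careful investigator would count an early rescue vasopressor without consulting the Appendix 1 window. Sites may in any case follow a case report form that asks for time from induction, and that form is not shown. This stands as a reason to expect little practical effect. It does not remove the contradiction, because Appendix 1 is the table of study definitions and no order of precedence is given.

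A second reply is that airway management could be taken to begin at preoxygenation, since Appendix 1 measures the duration of the procedure from there. The collapse window would then open before induction and the early discordance would go. But the window would also close early. If preoxygenation starts P minutes before induction, it ends at 30 − P minutes after induction, and collapses in the last P minutes of the primary window are lost unless incision has already ended it. That reading moves the conflict to the other end.

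A third reply is that the late example needs the window to end at whichever limit comes first, which only the early and late entries say. That is fair where incision comes after 30 minutes. Where there is no incision at all, 30 minutes is the only limit, and the example holds.

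**Conclusion.** The inconsistency is real for cardiovascular collapse, and it lies in current text. It should be corrected, but it is minor. The number of events affected cannot be computed, because the documents give neither L nor the timing of events. It is probably small: only episodes confined to the lag, or first arising just after 30 minutes without incision, are treated differently, and a collapse that persists past device use counts under both rules.

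Three stronger readings are tempting and are not supported.

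- *Cardiac arrest is in equal conflict.* Its entry has no timed window, so the primary outcome window supplies the limit. Only an arrest between induction and device use is arguably discordant.
- *A count of reclassified events can be given.* Spreading the 1,000 planned events evenly over 30 minutes with a 5-minute lag gives 1,000 × 5/30 = 167. A 1-minute lag at one quarter of the density gives 1,000 × 0.25/29.25 = 8.5. Lag and density are both assumed. The base includes severe hypoxia, which is not in conflict, and systolic pressure below 90 mmHg for more than 15 minutes, which cannot be completed in so short a gap unless incision falls in it. A density above that of the rest of the window is left out without support, so 167 is not even an upper bound.
- *The comparison of operating room with non-operating-room cases is distorted.* The incision cut-off already gives incised patients less observation time under the induction rule. With incision at 20 minutes (assumed), that is 20 minutes against 30. The inconsistency adds only the lag.

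**What to change.** In the Appendix 1 entry for cardiovascular collapse, start the window at induction and end it at 30 minutes or surgical incision, whichever comes first, as the early and late entries already do. Use the same wording in the Primary outcome section and the synopsis. This also settles which limit ends the primary window. For consistency, reword the cardiac arrest entry to *after induction, within the primary outcome window*. Leave the early/late split and the vasopressor definition as they are.

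The cost is a rewording of two Appendix 1 entries and of one phrase in two other places. The change asks for no timing beyond what the primary outcome and the early/late split already require, namely time from induction. The data collection list does not name that time or the event time, so the case report form should be checked for both. A collapse more than 30 minutes after induction would leave the Appendix 1 definition. Under the limit of whichever comes first, it is already outside the primary window.
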